The target population for this trial will be all kidney transplant candidates who are Black and placed on the active waiting list for a DDKT at SBMC. Whenever possible, at the initial transplant evaluation at SBMC or one of our satellite locations, we will “pre-consent” and explain the trial to potential transplant candidates who are Black and being evaluated for transplant. We will include potential transplant candidates who: ●identify themselves as Black; ●are ≥ 21 years of age; and ●give informed consent. We will exclude potential transplant candidates who ●have limited English proficiency or ●are unable (e.g. cognitive impairment) or unwilling to give informed consent. An overview of the study design can be found in Figure 1 below.

For the actual clinical trial, our inclusion and exclusion criteria are identical to the criteria for the Pre-consented group, with some additions. In the actual trial, we will include kidney transplant candidates who ●are placed on the DDKT waiting list; ●identify themselves as Black; ●are ≥ 21 years of age; and ●complete the baseline questionnaire; and exclude kidney transplant candidates who ●have limited English proficiency; ●are unable (e.g. cognitive impairment) or unwilling to give informed consent; ●lack a working telephone; ●live >150 miles from the transplant center; or ●were enrolled in our prior trial of an educational intervention at the time of the initial transplant evaluation¹⁷.

Randomization

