Patients who are eligible and consented to the study will be randomly assigned, after completing the baseline measurement, to either Usual Care or the Intervention, in a 1:1 allocation ratio. Randomization will occur in blocks of 8, using random numbers. Randomization will be stratified by whether the study participant is newly placed on the waiting list (defined as placement on the waiting list <6 months prior to enrollment) or has already been on the waiting list (defined as placement on the waiting list ≥6 months prior to enrollment). Random number sequences will be generated by the off-site study biostatistician ([name]). To promote allocation concealment, the biostatistician will allocate study participants to their study arm at the time of randomization and inform the study coordinator of the assigned study arm. The study coordinator will contact potentially eligible transplant candidates by telephone to inform them of their assignment. Study participants and the study coordinator will be aware of allocation to Usual Care or the Intervention group, but outcomes assessors will be blinded to the allocation group.

Study aims & objectives

The primary aim will compare LDKT readiness and LDKT receipt in the Intervention vs. Usual Care groups of our randomized clinical trial. Our primary outcome is change in readiness to pursue LDKT, and our main secondary outcome is actual receipt of LDKT after 18 months of follow-up. Other secondary aims will determine (a) the social and behavioral variables that modify the effect of the Intervention upon LDKT readiness and receipt; and (b) whether the intervention affects other precursors of LDKT readiness and receipt, such as knowledge about LDKT, self-efficacy, and other social and behavioral factors.

Data collection, follow-up and outcomes

Baseline Measurements

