After active placement on the waiting list, we will obtain “baseline” measurements of multiple social and behavioral attributes, via telephone questionnaires of all patients enrolled in the study (see Figure for flow of patients through the study). If we are unable to administer the baseline questionnaires within 2 months of enrollment into the trial (e.g. within 2 months of placement on the waiting list for newly listed patients, or within 2 months of consent for the patients already on the DDKT waiting list), then we will not randomize the patient. This requirement is intended to minimize later study dropout. Study participants will be mailed a \$25 gift card for this baseline measurement.

Follow-up Measurements: Timing

Each Usual Care study participant will be matched to one Intervention participant. For patients randomized to the Intervention, we will administer a follow-up questionnaire by telephone, approximately 1 week after the Intervention. At the same time, we will contact the matched Usual Care patient to administer the follow-up questionnaire. This procedure will ensure that the post-Intervention follow-up questionnaires are administered at approximately the same time, post-listing, for both Usual Care and Intervention patients, and using the same modality (telephone). A final administration of the study questionnaires will occur at 9 months after randomization for patients in both arms. We will provide \$25 gift cards for each of these two follow-up measurements.

Standard of Care Components (Usual Care/Control Group)

Participants who are randomized to receive the Usual Care engage in the standard education and evaluation process given to all patients at SBMC. While on the waiting list, transplant candidates are asked to inform the transplant center of important changes in their medical condition (e.g. hospitalizations) but otherwise typically have infrequent contact with the transplant center. Candidates return to the transplant center for periodic reevaluations by

transplant staff, usually every 1-2 years, depending upon the transplant candidate's medical comorbidities. At these reevaluations, transplant personnel usually discuss LDKT. These Usual Care patients will receive usual concomitant care but no additional formal education.

Intervention Components (“Destination Transplant”)

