Our initial analysis will be descriptive. Our main analysis will use standard intention-to-treat principles. First, we will describe participants’ baseline characteristics and compare

summary statistics of the Usual Care and Intervention groups. These summary statistics will include mean, standard deviation, median, and range for continuous variables, and counts and frequencies for categorical variables. Two-sample t-tests, Wilcoxon rank-sum tests (for non-parametric variables) and chi-squared tests will be used to test for differences between the Usual Care and Intervention groups, as appropriate.

For our primary outcome (increase in readiness to pursue LDKT), we will compare, using chi-square testing, the proportion of participants in the Usual Care vs. Intervention arms who have advanced at least one stage in their readiness to pursue LDKT (between the time of placement on waiting list and the time of reassessment at 18 months). For our main secondary outcome (receipt of LDKT), we will compare, using chi-square testing, the proportion of study participants in the Usual Care vs. Intervention arms who have received a LDKT. Sensitivity analyses will assess the intervention effect, adjusting for clustering of response by seminar group (because failing to account for clustering can reduce power)^{56,57}.

To determine which baseline factors (e.g. age), if any, modify the effect of the Intervention on the primary and secondary outcomes, logistic regression will model the log-odds of the outcome as a function of the intervention, while controlling for these factors of interest. Tests for modification by these key factors will be based on Wald tests of interaction terms between the intervention indicator and baseline factors. We will perform logistic regression⁵⁸ and model-building as we have in prior published analyses⁵⁹⁻⁶¹.

To test the effect of the intervention upon other precursors of LDKT readiness and receipt (e.g. knowledge about LDKT, self-efficacy, and other social and behavioral factors), we will use stratified chi-square tests for categorical variables and linear regression models for semi-continuous scales. The chi-square tests and linear regression models will be stratified by accumulated time on the waitlist at randomization (≤ 6 months vs. > 6 months). We will examine effects adjusted and unadjusted for baseline value for each respective scale.

Power and sample size calculations

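### The precursor analyses use a different 6-month waiting-list split from the one used to randomize, and the baseline-deadline wording does not clearly match either

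*Combined protocol and SAP*

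**What the plan says.** Three sections of the combined protocol and SAP use time on the waiting list.

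- **Randomization** defines two strata. One is "newly placed on the waiting list (defined as placement on the waiting list <6 months prior to enrollment"; the other is "already been on the waiting list (defined as placement on the waiting list ≥6 months prior to enrollment". The reference date is enrollment, and exactly 6 months falls in the longer group. The same section places random assignment after the baseline measurement.
- **Baseline Measurements** withholds randomization when staff are "unable to administer the baseline questionnaires within 2 months of enrollment into the trial". An example in parentheses then gives two clocks. The first starts at listing: "within 2 months of placement on the waiting list for newly listed patients". The second starts at a different date, that of consent: "within 2 months of consent for the patients already on the DDKT waiting list". The consequence of missing the deadline is "then we will not randomize the patient".
- **Statistical analyses** says that the chi-square tests and linear regressions for the other precursors of readiness and receipt are "stratified by accumulated time on the waitlist at randomization (≤ 6 months vs. > 6 months". The reference date is now randomization, and exactly 6 months falls in the shorter group.

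Study population targets "all kidney transplant candidates who are Black and placed on the active waiting list for a DDKT at SBMC" and sets no limit on time since listing. Consent before listing is sought only where possible, so the plan allows for candidates who first consent once listed.

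**The concern.** A stratified analysis is normally run on the strata within which patients were randomized, because balance between arms was enforced there (here in blocks of 8). The precursor analyses instead use a different date and a different side of the 6-month boundary. Some patients could therefore change stratum between allocation and analysis.

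The baseline deadline adds a second difficulty. Its two clocks carry labels close to those of the two strata, but Baseline Measurements does not define them, and the only definitions in the documents are those in Randomization. Enrollment fixes both the stratum and the deadline, yet it is explained only through the example in parentheses. Staff could start the clock on different dates for the same kind of patient. At stake are consistent entry to the trial and, for the secondary precursor analyses, agreement between design and analysis.

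**Working it through.** The plan gives no figure to reproduce here; the check is a timeline.

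**Inputs.** The stratum cut for allocation (under 6 against 6 or more months, at enrollment) comes from Randomization. The cut for analysis (6 or less against more than 6 months, at randomization) comes from Statistical analyses. The 2-month limit comes from Baseline Measurements. Let L be months from listing to enrollment and t months from enrollment to randomization. Assume randomization follows baseline at once, so t is at most 2; the documents set no limit on that last gap.

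**Step 1: do the two splits agree when the clock runs from consent?** The allocation stratum depends on L, the analysis stratum on L + t.

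| L | t | L + t | Randomized as | Analysed as | Agree? |
|---|---|---|---|---|---|
| 3 | 2 | 5 | <6 | ≤6 | yes |
| 4 | 2 | 6 | <6 | ≤6 | yes (limit) |
| 4.5 | 2 | 6.5 | <6 | >6 | **no** |
| 5 | 0.5 | 5.5 | <6 | ≤6 | yes |
| 5 | 1.5 | 6.5 | <6 | >6 | **no** |
| 6 | 0 | 6 | ≥6 | ≤6 | **no** |
| 7 | 1 | 8 | ≥6 | >6 | yes |

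The splits disagree when L < 6 and L + t > 6. With t ≤ 2 this needs L > 6 − 2 = 4, so the range at risk is more than 4 and under 6 months. Any delay between baseline and randomization extends it downward, starting with patients at exactly 4 months. In the other direction, only a patient at exactly 6 months who is randomized the same day changes group.

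**Step 2: the same check when the clock runs from listing.** Baseline is then done by month 2 after listing. Passing 6 months before randomization would need a further delay of more than 6 − 2 = 4 months, so the mismatch has almost no practical effect. Patients who consented before listing are in this position.

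**Step 3: the baseline window under two readings.** For a candidate first consented L months after listing, the time left for baseline is:

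| L | Randomization definitions applied to the deadline | Clock from consent for anyone already listed |
|---|---|---|
| 0 | 2 | 2 |
| 1 | 2 − 1 = 1 | 2 |
| 2 | 2 − 2 = 0 | 2 |
| 3 | 2 − 3 = −1 | 2 |
| 5.9 | 2 − 5.9 = −3.9 | 2 |
| 6 or more | 2 | 2 |

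The first reading closes the window for L above 2 and below 6, then reopens it at 6. The second closes it for nobody, but the same patient is then already listed for the deadline and newly placed for the stratum.

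**Step 4: which tests use the split?** Statistical analyses attaches it only to the precursor tests. Readiness and receipt of a living donor transplant are compared by chi-square tests with no stratification stated.

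**The case against.** A reader might infer that candidates listed 2 to 6 months before consent cannot be randomized, and that the site must turn them away. The documents do not support this. The operative rule is 2 months from enrollment; the listing and consent clocks are only examples of it. In ordinary words, someone listed 4 months before consenting is already on the list, and so has 2 months from consent. That reading also fits the two entry routes implied by Study population: consent at evaluation before listing, or first consent while listed. The patient-flow figure, not shown in the text available, may make those routes explicit.

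A reader might also take the closed part of the window, (6 − 2)/6 = 67%, as a share of patients lost. It is a share of calendar time under one reading, and the documents give no distribution of consent times. Nor does the 6-month cut become empty if listing counts as enrollment for those who consented earlier: it still separates late consenters at, say, 3 and 7 months.

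The remaining objection is that the mismatch in the analysis strata is small. That is largely right. It touches secondary analyses only, and the boundary difference alone matters only at exactly 6 months. Time on the list at randomization is also fixed before allocation, so regrouping by it does not itself bias the comparison of arms. What stands against the plan is that the analysis strata are not the randomized strata, and no reading makes the three sections agree.

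**Conclusion.** The point holds as an inconsistency of definition with limited reach. The allocation and analysis splits differ in both date and boundary. Under a consent-based clock, patients enrolled more than 4 and under 6 months after listing can be analysed outside their randomized stratum. This affects the precursor analyses; the primary and main secondary tests are untouched.

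The stratum and deadline labels also need reconciling, but the documents show an ambiguity and not an exclusion. The two consequences do not occur together for the same patient: a listing-based clock closes the window and nearly removes the stratum mismatch, while a consent-based clock does the reverse. The number affected under either reading cannot be estimated from the documents. The 4-month lower limit assumes that randomization follows baseline without delay.

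**What to change.** 1. In Statistical analyses, replace the split for the precursor tests with the stratum actually used at randomization: listed under 6 months, or 6 months or more, before enrollment.
2. Define enrollment once, in Randomization or Baseline Measurements: the listing date for patients who consented before listing, and the consent date for everyone else. Run the 2-month baseline clock from that date in both strata, and remove or reword the example so that its labels match the stratum definitions.
3. If recruitment is complete, state which starting date was used in practice for patients first consented under 6 months after listing, and make the first change regardless.

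The cost is a few sentences. The randomized stratum was needed to allocate each patient, so no new data are required.

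### A cheap improvement, not an error: test readiness and LDKT receipt within the randomization stratum, and readiness also by top baseline stage

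*Combined protocol and SAP*

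**What the plan says.** All references are to the combined protocol and SAP.

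- **Statistical analyses, primary outcome (readiness):** "we will compare, using chi-square testing, the proportion of participants in the Usual Care vs. Intervention arms who have advanced at least one stage".
- **Statistical analyses, main secondary outcome:** a chi-square test of "the proportion of study participants in the Usual Care vs. Intervention arms who have received a LDKT". No stratum or covariate is named for either test.
- **Randomization:** "Randomization will be stratified by whether the study participant is newly placed on the waiting list", that is, listed under 6 months before enrollment, or already listed, "defined as placement on the waiting list ≥6 months prior to enrollment". Allocation follows baseline assessment: "Patients who are eligible and consented to the study will be randomly assigned, after completing the baseline measurement". Table 2 marks Stage of Change at baseline. Both variables are therefore known before assignment.
- **Statistical analyses, other models for the two main outcomes:** "Sensitivity analyses will assess the intervention effect, adjusting for clustering of response by seminar group"; and, for effect modification, "logistic regression will model the log-odds of the outcome as a function of the intervention, while controlling for these factors of interest". Neither names the listing stratum or the baseline stage.
- **Statistical analyses, precursor outcomes only:** tests and models are "stratified by accumulated time on the waitlist at randomization (≤ 6 months vs. > 6 months"), with results shown both with and without adjustment for the baseline value of each scale.

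**The concern.** The lower-ranked outcomes get a more efficient analysis than the primary and main secondary outcomes. Two things are lost.

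1. Randomization balances the arms on listing time. If listing time predicts the outcome, the crude test counts between-stratum variation as error and gives up some power.
2. A participant at the top stage at baseline cannot advance, and the eligibility criteria do not exclude such participants. They carry no information about the treatment effect on this endpoint, but a chance imbalance in their number moves the crude difference.

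Power is the only thing at stake, and Table 3 is thin in places: 0.76 for readiness 0.10 v 0.20 at 200 per arm, and 0.78 and 0.68 for LDKT 0.14 v 0.24 at 250 and 200 per arm.

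**Working it through.** **Inputs.** From Power and sample size calculations and Table 3: 250 or 200 per arm, readiness 0.10 to 0.40 in controls, LDKT 0.14 in controls, and the listed intervention rates. Not in the documents, so assumed: two-sided alpha 0.05, stratum sizes and stratum effects, and the share c at the top stage.

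**Step 1: reproduce Table 3.** Power = Φ{[d − 1.96√(2P(1−P)/m)] / √([p1(1−p1) + p2(1−p2)]/m)}, where d = p2 − p1, P is the mean rate and m = (n − 1/d)²/n is the continuity-corrected size. For LDKT 0.14 v 0.24 at n = 250, m = 240²/250 = 230.4 and power = Φ[(0.10 − 1.96 × 0.03655)/0.03625] = Φ(0.78) = 0.78, as printed. All 18 entries agree within 2 points. Below, both tests are uncorrected. Crude power is then about 1 to 5 points above Table 3, so read the gains, not the levels.

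**Step 2: LDKT by listing stratum.** The stratified test replaces the null variance 2P(1−P)/n by Σ w_k·2p̄_k(1−p̄_k)/n, where w_k is the share in stratum k and p̄_k its mean rate over the arms. Example at 250 per arm: equal strata, control rates 0.20 and 0.08 (mean 0.14; odds ratio 0.25/0.087 = 2.9), and a common treatment odds ratio giving 0.332 and 0.148 (mean 0.24).
- Crude: Φ[(0.10 − 1.96 × 0.03509)/0.03410] = Φ(0.916) = 0.820.
- Stratified: Φ[(0.10 − 1.96 × 0.03442)/0.03410] = Φ(0.954) = 0.830, a gain of 1.0 point.

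Simulated gains (200,000 trials per setting) at stratum odds ratios 1, 1.5, 2 and 3 are 0.0, +0.1, +0.4 and +1.1 points at 250 per arm, and −0.4, −0.1, +0.3 and +1.1 at 200. Only extreme strata do better: control rates 0.24 and 0.04 give 2.8 points at 250 and 3.4 at 200 (3.7 by formula). At 0.14 v 0.29 the gain is at most about 1 point with moderate strata.

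**Step 3: readiness by top stage.** Table 3 rates are held for all participants, so the rate among those able to advance is p/(1−c). Example, 0.40 v 0.55, 200 per arm, c = 0.20: rates 0.40/0.80 = 0.50 and 0.55/0.80 = 0.6875, mean 0.594.
- Crude: Φ[(0.15 − 1.96 × 0.04994)/0.04937] = Φ(1.056) = 0.854.
- Stratified: null variance 0.80 × 2 × 0.594 × 0.406/200, standard error 0.04393; Φ[(0.15 − 1.96 × 0.04393)/0.04312] = Φ(1.482) = 0.931, a gain of 7.6 points.

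Simulated gains in points, stratifying on top stage alone:

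| Rates | n per arm | c = 10% | 20% | 30% |
|---|---|---|---|---|
| 0.10 v 0.20 | 250 | 0.6 | 1.3 | 2.2 |
| 0.10 v 0.20 | 200 | 0.5 | 1.4 | 2.5 |
| 0.25 v 0.40 | 250 | 0.9 | 2.1 | 3.2 |
| 0.25 v 0.40 | 200 | 1.4 | 3.4 | 5.4 |
| 0.40 v 0.55 | 250 | 1.8 | 4.4 | 6.5 |
| 0.40 v 0.55 | 200 | 3.3 | 7.5 | 11.6 |

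Crossing top stage with the listing stratum (four cells) gives, over these rates and sizes, −0.4 to 0.0 with nobody at the top, +0.1 to +1.4 at 5%, +0.4 to +3.3 at 10% and +1.2 to +7.5 at 20%. The three larger-effect rows (0.10 v 0.30, 0.25 v 0.45, 0.40 v 0.60) gain at most about 1.5 points at 20%, because their power is already 0.98 or more.

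**Step 4: type I error.** Without clustering, the stratified tests hold 0.048 to 0.051. The crude LDKT test falls to 0.046 to 0.047 at a stratum odds ratio of 3. With seminars of 4 (the protocol expects 3 to 5 candidates) and an assumed intraclass correlation of 0.05, the Intervention arm's variance rises by 1 + 3 × 0.05 = 1.15, or 1.075 averaged over the arms. Crude alpha becomes 2[1 − Φ(1.96/√1.075)] = 0.059. At 0.10 the factors are 1.30 and 1.15, and alpha is 0.068. Simulation gives about 0.055 to 0.059 and 0.065 to 0.067.

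**The case against.** **The plan names an acceptable test, and Table 3 is powered on two raw proportions.** This stands. A reader might infer that stratified randomization makes the crude chi-square invalid. It does not: ignoring a prognostic stratum makes the test slightly conservative. That statement in turn holds only with seminar clustering set aside. Step 4 shows that modest clustering could push alpha up by more than the stratum pulls it down, and the stratified test does nothing about this.

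**The gain rests on assumptions.** This also stands. No stage distribution, stratum size or stratum-specific rate is given. The 7-point and 12-point figures are both from one row (0.40 v 0.55, 200 per arm) at assumed shares of 20% and 30%. A reader might take them as the expected gain or as an upper bound; the documents support neither.

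**The sentence about stratifying the chi-square tests might cover every test.** A generous reader could say so, but it sits in the precursor paragraph and follows on from the tests named there. If the wider meaning was intended, one line would settle it.

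**The 6-month cut-points differ.** Randomization uses <6 v ≥6 months before enrollment; the precursor analyses use ≤6 v >6 months at randomization. A reader might infer that patients are analysed in the wrong stratum. Baseline Measurements, however, ties enrollment of newly listed patients to placement on the list and allows 2 months for the baseline questionnaire. On that reading few or no patients would change stratum.

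**A late change to a primary test can look post hoc.** The document is dated December 2019 and parts of Measures are in the past tense. This is a fair caution about timing, and the reason to date the amendment before outcomes are compared by arm.

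**Conclusion.** The point holds as an optional improvement in efficiency. For LDKT receipt the benefit is about a point or less unless the strata differ sharply; the case there is mainly consistency with the design. For readiness it depends on how many participants start at the top stage: close to nothing if few do, and several points in the smaller-effect rows if about a fifth do. Confidence in the direction is good. Confidence in the size is limited, because stratum effects and top-stage shares are assumed and no power run includes seminar clustering.

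**What to change.** First reconcile the readiness time point: Statistical analyses says 18 months, while Table 2 has no readiness measure after 9 months. Name one of the two instruments described under the readiness measures. Then, in a dated amendment before outcomes are compared by arm:

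- **LDKT receipt:** Cochran-Mantel-Haenszel (CMH) test by the recorded randomization stratum (<6 v ≥6 months).
- **Readiness:** CMH test by that stratum and top baseline stage (yes/no). An ordinary logistic model with top stage as its own category cannot estimate that coefficient, because nobody there can advance; CMH has no such difficulty. Stratifying on every stage (five assumed) costs about 1 point if stage does not matter, so yes/no is the safer default.
- **Estimate:** report the all-participant proportions and the risk difference standardised over the same cells, Σ(N_k/N)(p_Ik − p_Ck), with its interval. This keeps the comparison of all participants. For readiness, in simulation, it disagreed with the four-cell CMH test at 5% in at most 0.5% of trials, against up to 9.4% for the unstandardised difference.
- **Supporting result:** keep the crude chi-square.
- **Precursor analyses:** use the recorded randomization stratum.
- **Clustering:** keep the planned seminar-clustering analysis; nothing here replaces it.

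The cost is the amendment itself and up to about 0.4 points of power if neither factor matters. No new data, patients or change in conduct are needed.
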